12.1.2 Hypothesis Testing

Primary hypothesis testing on the odds ratio: The null hypothesis is that the vIGA-AD success does not differ between roflumilast cream 0.05% and matching vehicle cream. The alternative hypothesis is that the vIGA-AD success does differ between roflumilast cream 0.05% and matching vehicle cream.

Null Hypothesis (H_0): $P_R Q_V / P_V Q_R = 1.0$,

Alternative Hypothesis (H_A): $P_R Q_V / P_V Q_R \neq 1.0$, where

P_R = the proportion of vIGA-AD success in roflumilast cream 0.05%

P_V = the proportion of vIGA-AD success in matching vehicle cream

$Q_R = 1 - P_R$

$Q_V = 1 - P_V$.

12.1.3 Primary Endpoint Analysis

For the primary analysis, missing vIGA-AD scores will be imputed using multiple imputation as described in Section 6.2.1. These imputations will result in a minimum of 25 to a maximum of 250 complete analysis datasets, depending on the number of imputed monotone datasets that are required.

Percentages of subjects having a vIGA-AD Success (refer to Section 12.1.1) will be presented by visit and treatment group based on multiply imputed data in the ITT population along with both 97.5% and 95% Wilson CIs. The common MH odds ratio and common MH proportion difference, adjusted for the randomization factor (i.e., randomized vIGA-AD score) will also be provided along with their common associated 97.5% and 95% CIs. Additionally, count and percentage of subjects having a vIGA-AD success, count and percentage of subjects in each category of the vIGA-AD scale, and descriptive statistics for the vIGA-AD scores, change in vIGA-AD score from baseline and percent change in vIGA-AD score from baseline will be presented by visit and treatment group based on observed data in the ITT population.

The primary endpoint (vIGA-AD Success at Week 4) will then be analyzed using multiple imputation CMH test stratified by randomized baseline vIGA-AD. To do so, a CMH analysis will be performed separately for each of the complete multiply imputed analysis data sets, and results will be combined into one multiple imputation inference using the methodology described in Section 6.2.1. Statistical significance will be concluded at the 2.5% significance level (2-sided). Should the odds ratio be not estimable for at least one multiply imputed dataset, the conclusion of

 Innovaderm Research ■■■	STATISTICAL ANALYSIS PLAN, Version 1.0
Protocol Number: ARQ-151-315	Sponsor: Arcutis Biotherapeutics, Inc.

the study will be based on the p-value obtained from a MH test, stratified by randomized baseline vIGA-AD, for the common MH proportion difference at Week 4.

The following sensitivity and supplemental analyses to the primary analysis of the primary endpoint will be performed:

- Tipping Point analysis (refer to Section [6.2.3](#)) on ITT population.
- Non-responder imputation (refer to Section [6.2.2](#)) on ITT population.
- Observed data on ITT population (refer to Section [4.1](#)).
- Observed data on PP population (refer to Section [4.2](#)).

For the last three sensitivity/supplemental analyses, count of subjects having vIGA-AD success will also be presented by visit and treatment group in addition to the percentage of subjects having vIGA-AD success.

To assess the impact of individual study sites on the primary analysis of the primary endpoint, the following analyses will be performed:

- To assess the impact of site on the primary analysis endpoint, the proportion of subjects achieving vIGA-AD success and 97.5% CI within each site with at least 10 randomized subjects will be tabulated. No p-values will be provided. Forest plots of the proportions (and associated 97.5% CI) for each site with at least 10 randomized subjects, by treatment, will also be provided.
- An additional analysis to examine the impact of study site will examine the changes in p-values that occur after removal of sites that randomized at least 10 subjects. To do so, the primary analysis of the primary efficacy endpoint will be repeated by removing a different study site for each iteration. Forest plots of the odds ratio (and associated 97.5% CI) for each analysis will also be provided.

12.2 Secondary Efficacy Endpoints Analysis

Secondary efficacy endpoints are based on the vIGA-AD scale or EASI questionnaire. The list of secondary efficacy endpoints can be found in Section [2](#) and their derivation in Section [5.5](#).

- For more details about the vIGA-AD scale refers to Section [12.1.1](#).
- For the EASI questionnaire, four anatomic sites (head, upper extremities, trunk, and lower extremities) are assessed for erythema, induration/infiltration (papules), excoriation, and

 Innovaderm Research	STATISTICAL ANALYSIS PLAN, Version 1.0
Protocol Number: ARQ-151-315	Sponsor: Arcutis Biotherapeutics, Inc.

lichenification as seen on the day of the examination. The severity of each sign is assessed using a 4-point scale (half steps are allowed e.g., 0.5): 0 (none), 1 (mild), 2 (moderate), and 3 (severe). The area affected by AD within a given anatomic site is estimated as a percentage of the total area of that anatomic site and assigned a numerical value according to the degree of AD involvement as follows: 0 (no involvement), 1 (1-9%), 2 (10-29%), 3 (30-49%), 4 (50-69%), 5 (70-89%), and 6 (90-100%).

For each secondary efficacy endpoint, missing data will be imputed and data will be summarized as for the primary efficacy endpoint (refer to Section 12.1.3).

Upon successful demonstration of statistical significance for the primary efficacy endpoint, the secondary efficacy endpoints will be tested sequentially at an alpha level of 0.025.

The secondary efficacy endpoint of vIGA-AD success among subjects with vIGA-AD score of ‘Moderate’ at randomization will be analyzed as described for the primary efficacy endpoint (refer to Section 12.1.3) but based on the vIGA-AD Moderate ITT population (refer to Section 4.3) and use of a chi-square test to evaluate the treatment effect. That is, as per the vIGA-AD Moderate ITT population definition all subjects included in this analysis will have a randomized vIGA-AD score of Moderate (3) and so, the CMH test cannot be used.

The remaining secondary efficacy endpoints, comprised of the endpoints of EASI-75 at Week 4, vIGA-AD of ‘clear’ or ‘almost clear’ at Week 4, vIGA-AD of success at Week 2, vIGA-AD of ‘clear’ or ‘almost clear’ at Week 2, vIGA-AD of success at Week 1 and vIGA-AD of ‘clear’ or ‘almost clear’ at Week 1 will be performed as described for the primary efficacy endpoint (refer to Section 12.1.3) based on the ITT population (refer to Section 4.1).

For the secondary efficacy endpoint of vIGA-AD Success at Week 4 based on the vIGA-AD moderate ITT population, the following sensitivity analyses to the primary analysis of this efficacy endpoint will be performed:

- Non-responder imputation (refer to Section 6.2.2) on vIGA-AD moderate ITT population.
- Observed data on vIGA-AD moderate ITT population.

For these sensitivity analyses, count of subjects having vIGA-AD success will also be presented at Week 4 by treatment group in addition to the percentage of subjects having vIGA-AD success.

For all other secondary efficacy endpoints, the following sensitivity analyses to the primary analysis of these secondary endpoints will be performed:

- Non-responder imputation on ITT population.

 Innovaderm Research ■■■	STATISTICAL ANALYSIS PLAN, Version 1.0
Protocol Number: ARQ-151-315	Sponsor: Arcutis Biotherapeutics, Inc.

- Observed data on ITT population.

The EASI total score and EASI-75 flag at each visit will be listed.

12.3 Exploratory Efficacy Endpoints Analysis

Exploratory efficacy endpoints are based on the vIGA-AD scale, EASI questionnaire, WI-NRS scale, %BSA affected by AD, CDLQI/IDQoL questionnaires, DFI questionnaire, SCORAD tool or POEM tool. The list of other efficacy endpoints can be found in Section 2 and their derivation in Section 5.5.

- For more details about the vIGA-AD scale, refer to Sections 12.1.1.
- For more details about the EASI questionnaire, refer to Section 12.2.
- For more details about the WI-NRS scale, refer to Section 5.5.
- The % of BSA affected by AD will be determined by the subject's hand method, where the subject's hand (including fingers) surface area is assumed to equal 1% of BSA (excluding the scalp, palms, and soles).
- The CDLQI is a self-administered validated questionnaire designed to measure the health-related quality of life of children subjects (≥ 4 years old) suffering from a skin disease. It consists of 10 questions concerning subjects' perception of the impact of skin disease on different aspects of their health-related quality of life over the last week. Questions 1 to 6 and 8 to 10 are rated from 0 (Not at all) to 3 (Very much). For question 7, if last week was a school time, question 7 is rated from 0 (Not at all) to 3 (Prevented school) but if the last week was a holiday time, question 7 is rated from 0 (Not at all) to 3 (Very much).
- The IDQoL questionnaire is designed to assess the impact of atopic dermatitis on the quality of life of infants < 4 years old. It is self-explanatory and should be completed by the child's parent(s) or regular caregiver and consists of 10 questions rated from 0 to 3. The severity of dermatitis is scored separately, and it is not included in the IDQoL total score.
- The DFI questionnaire measures how much having a child with AD affects the quality of life of other (adult) members of the family over the last week. It is designed to be completed by parents/caregivers and consists of 10 questions rated from 0 (Not at all) to 3 (Very much).
- The SCORAD is a clinical tool to assess the severity (i.e., extent, intensity) of AD as objectively as possible. First, the overall %BSA affected by AD is evaluated (from 0% to

 Innovaderm Research	STATISTICAL ANALYSIS PLAN, Version 1.0
Protocol Number: ARQ-151-315	Sponsor: Arcutis Biotherapeutics, Inc.

100%, where a subject's palm represents 1% of his/her total BSA). Secondly, the AD severity is evaluated based on 6 items (erythema, edema/papulation, oozing/crusts, excoriation, lichenification, and dryness) graded using a 4-point scale (half steps are not allowed): 0 (absence), 1 (mild), 2 (moderate), and 3 (severe). Lastly, 2 subjective items (loss of sleep and intensity of pruritus) are evaluated by having the subject indicates on a 10.0 cm visual analog scale (VAS) the point corresponding to the average value over the last 3 days (0 cm = none to 10 cm= maximum).

- The POEM is a tool used for monitoring atopic eczema severity. It focus on the illness as experience by the subject. It consists of a 5-point scale measuring the frequency of each of 7 AD symptoms (i.e., dryness, itching, flaking, cracking, sleep loss, bleeding, and weeping) over the past week scored from 0 (no days), 1 (1 to 2 days), 2 (3 to 4 days), 3 (5 to 6 days), and 4 (every day).

For subjects who discontinue due to lack of efficacy or adverse event, efficacy data assigned to a pre-specified analysis visit will be removed from observed data if subject's last dose day falls within the analysis visit window or is prior to the start of the analysis visit window used to assign data to a pre-specified analysis visit. This will be true for all endpoints described above.

For the continuous exploratory efficacy endpoints of change and percent change from baseline in average weekly WI-NRS, EASI total score, % BSA, CDLQI/IDQoL score (+ severity of dermatitis), DFI score, SCORAD score, and POEM score at Week 1, Week 2, Week 3 (WI-NRS only), and Week 4, descriptive statistics for the score, change from baseline and percent change from baseline will be presented by visit and treatment group based on observed data in the ITT population. For the continuous other efficacy endpoint of daily WI-NRS, descriptive statistics will also be presented similarly on a daily basis. Additionally, a plot of the mean (and standard error) daily WI-NRS scores over time for each treatment group will also be provided based on observed data. A similar plot will be provided for the percent change from baseline in daily WI-NRS.

Continuous exploratory efficacy endpoints will be analyzed at Week 1, Week 2, Week 3 (WI-NRS only), and Week 4 and for daily WI-NRS assessments using an analysis of covariance (ANCOVA) with the factors of treatment, randomized vIGA-AD score, and baseline of the variable under analysis as covariate. The Least Square (LS) mean and its standard error, difference in LS means between treatment group (i.e., active - vehicle), its standard error and associated 97.5% and 95% confidence interval, and p-value for difference from vehicle will be presented at each visit. These analyses will be performed based on observed data in the ITT population.

Exploratory categorical endpoints based on vIGA-AD, EASI, or WI-NRS, ie VIGA-AD score of clear, EASI-50, EASI-75, EASI-90, EASI-100, WI-NRS success in the WI-NRS population, will

 Innovaderm Research ■■■	STATISTICAL ANALYSIS PLAN, Version 1.0
Protocol Number: ARQ-151-315	Sponsor: Arcutis Biotherapeutics, Inc.

be analyzed by visit and treatment group based on MI data and the ITT population with the same methods used for related primary or secondary endpoints. For all categorical exploratory efficacy endpoints, count and percentages of subjects meeting the criteria for exploratory efficacy endpoints will be presented by visit and treatment group based on observed data in the ITT population along with a 97.5% and 95% Wilson CI. The observed data will also be analyzed using a CMH test adjusted for randomized vIGA-AD score. Common MH odds ratio, common MH proportion difference and their common associated 97.5% and 95% CIs, adjusted for the randomized vIGA-AD score, will be provided. The p-value will be from a CMH test, unless the common MH odds ratio is not estimable. In such circumstances, the p-value will be from a MH test for the common MH proportion difference.

The p-values will be nominal as no formal inferential testing will be done on exploratory efficacy endpoints.

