2 STUDY OBJECTIVES AND ENDPOINTS

OBJECTIVES	ENDPOINTS
Efficacy	
To assess the efficacy of ARQ-151 cream 0.05% vs vehicle administered once daily (QD) x 4 weeks to subjects aged 2-5 years with atopic dermatitis (AD).	
Primary efficacy endpoint:
 
 Validated Investigator Global Assessment scale for Atopic Dermatitis (vIGA-AD) Success, defined as a vIGA-AD score of 'clear' (0) or 'almost clear' (1) plus at least a 2-grade improvement from Baseline at Week 4 
Secondary efficacy endpoints:
 
 In subjects with a vIGA-AD score of 'Moderate' at randomization, vIGA-AD Success at Week 4 Achievement of at least a 75% reduction in the Eczema Area and Severity Index (EASI-75) at Week 4 vIGA-AD of 'clear' or 'almost clear' at Week 4 vIGA-AD Success at Week 2 vIGA-AD of 'clear' or 'almost clear' at Week 2 vIGA-AD Success at Week 1

 Innovaderm Research ■■■	STATISTICAL ANALYSIS PLAN, Version 1.0
Protocol Number: ARQ-151-315	Sponsor: Arcutis Biotherapeutics, Inc.

OBJECTIVES	ENDPOINTS
	
 • vIGA-AD of 'clear' or 'almost clear' at Week 1 
Exploratory efficacy endpoints:
 
 • Exploratory continuous efficacy endpoints include change and percent change in average weekly WI-NRS and daily WI-NRS, EASI, % body surface area (BSA) affected by AD, Children's Dermatology Life Quality Index (CDLQI)/Infant's Dermatitis Quality of Life Index (IDQoL), the Dermatitis Family Impact (DFI), Scoring Atopic Dermatitis (SCORAD), and Patient-oriented Eczema Measure (POEM) at Week 1, Week 2 and Week 4. • Exploratory categorical efficacy endpoints include EASI-75 at Week 1 and Week 2; EASI-50, EASI-90, EASI-100, achievement of at least a 4-point reduction on the WI-NRS, and vIGA-AD of 'clear' at Week 1, Week 2 and Week 4.
Safety	
To assess the safety of ARQ-151 cream 0.05% vs vehicle administered QD x 4 weeks to subjects aged 2-5 years with AD.	
 • Incidence and severity of adverse events (AEs) • Changes and percent change in vital signs • The subject incidence of $\geq 5\%$ weight loss or gain on study • Local tolerability assessments

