- d. The vIGA-AD assessment will be a 5-point scale ranging from clear (0) to severe (4) and is evaluated for the entire body except the scalp, palms, and soles. EASI takes into account overall severity of erythema, infiltration/papulation, excoriation, and lichenification, in addition to extent of BSA affected. The 4 clinical signs will be graded on a 4-point scale (0 [absent] to 3 [severe]) for 4 body regions (head and neck, upper extremities, lower extremities, and trunk). Total EASI score will be calculated as a sum of scores of all 4 body regions. EASI total score will range from 0 (absent) to 72 (severe). Total BSA affected by AD will be determined for all body surfaces except the scalp, palms and soles. **The vIGA-AD assessment should be completed prior to other physician assessments.** SCORAD total score will range between 0 and 103.
- e. Parents/guardians/caregivers of children will report pruritus at home on a daily basis starting 7 days prior to the Baseline/Day 1 visit, and then every day thereafter using a diary. WI-NRS score will be determined by assessing worst itch over the past 24 hours. The scale is from 0 (no itch) to 10 (worst itch) and this value will be recorded each day. Caregiver/parents will be given instructions on how to complete this questionnaire.
- f. POEM will be completed for all subjects by proxy completion.
- g. Local tolerability assessments should be recorded prior to study drug application for the Investigator assessment of skin irritation (Berger and Bowman skin irritation score) and 10-15 minutes post-drug application for the Subject's '0-3' burning/stinging assessment. Parents/guardians will complete assessment for subjects. Subject's burning/stinging assessment at Week 4/Day 29 will be provided by a recall assessment of burning/stinging experienced post drug application on the previous day (Day 28). **Note for Investigator tolerability assessments: reactions at the site of product application, which may occur post-Baseline, should be differentiated from the preexisting inflammation associated with the subject's atopic dermatitis.** If a subject is entering ARQ-151-313 Open Label Extension study, then the Subject's '0-3' burning/stinging assessment will be performed as described in the ARQ-151-313 protocol for Baseline/Day 1.

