4.4 WI-NRS Population

WI-NRS population will be a subset of the ITT population who:

1. Parent/caregiver completed at least 4 of 7 evaluable daily WI-NRS questionnaires during the last 7 days of the Screening period.
2. Have a mean baseline WI-NRS score ≥ 4.0 , defined as the average of all non-missing scores reported during the last 7 days of the Screening period if at least 4 of 7 evaluable daily WINRS questionnaires available. If 4 or more evaluable daily questionnaires are missing, then the baseline score will be treated as missing.

All subjects will be analyzed according to the treatment group and stratum to which they were randomized.

 Innovaderm Research ■■■	STATISTICAL ANALYSIS PLAN, Version 1.0
Protocol Number: ARQ-151-315	Sponsor: Arcutis Biotherapeutics, Inc.

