5.2 Baseline

Unless otherwise specified, baseline value will be defined as the last non-missing assessment prior to or concurrently with the first study treatment application (including unscheduled/retest assessments). The randomization date will be used in place of the date of first treatment application for randomized subjects who discontinue without having treatment applied. If the last non-missing assessment is performed on the same date as the first study treatment administration and time is not available, it is assumed that the assessment took place prior to IP application, per study site training, and the assessment will be considered as baseline, except for adverse events (AEs) and medications starting on the first study treatment dose administration date which will be considered postbaseline.

Average weekly baseline WI-NRS is defined as the average of all non-missing scores reported during the last 7 days prior to treatment if at least 4 of 7 evaluable daily WI-NRS questionnaires available. Daily baseline WI-NRS is defined as the last non-missing assessment prior to or concurrently with the first study treatment dosing. Day 1 WI-NRS score will be used to calculate the value for week 1 only when it is collected after the application of the first study drug. If Day 1 WI-NRS score is collected prior to or concurrently with the application of the first study drug, then the Day 1 WI-NRS score will be included in baseline calculation.

For investigator/subject tolerability assessments, baseline is derived as the measurement taken on the day of first application of study drug.

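### The exploratory daily itch ANCOVA has a single diary score as its only itch covariate; adding the 7-day baseline mean could gain some precision.

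*SAP*

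**What the plan says.** SAP section 2 lists "change and percent change in average weekly WI-NRS and daily WI-NRS" among the exploratory continuous endpoints. SAP 12.3 fits all of these, at each visit and for each day of the itch diary, by ANCOVA "with the factors of treatment, randomized vIGA-AD score, and baseline of the variable under analysis as covariate". On the data used it says: "These analyses will be performed based on observed data in the ITT population". The resulting p-values are declared nominal.

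SAP 5.2 fixes what baseline means for itch. For the daily series: "Daily baseline WI-NRS is defined as the last non-missing assessment prior to or concurrently with the first study treatment dosing". For the weekly series: "Average weekly baseline WI-NRS is defined as the average of all non-missing scores reported during the last 7 days prior to treatment", with the condition "if at least 4 of 7 evaluable daily WI-NRS questionnaires available". SAP 4.4 gives the consequence when diaries are lacking: "If 4 or more evaluable daily questionnaires are missing, then the baseline score will be treated as missing".

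The pre-treatment diaries are collected in any case. The schedule in SAP 3.2 states that caregivers "will report pruritus at home on a daily basis starting 7 days prior to the Baseline/Day 1 visit". SAP section 8 tabulates both itch baselines. The documents give no reason for using only the single score in the daily model.

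**The concern.** ANCOVA gains precision through the correlation between covariate and outcome. One 0-10 caregiver rating of one day's worst itch contains day-to-day noise. A mean of up to seven such ratings contains less, and will often predict a later day's score better than one rating does. The weekly itch ANCOVA already has the average as its baseline; the daily ANCOVA does not.

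At stake is the width of the intervals around the daily treatment differences, the SAP's only day-level comparison of itch. No primary or secondary endpoint is involved, and no decision rule depends on it.

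**Working it through.** **Figures in the plan.** The documents state no SD, reliability, within-child correlation or diary completion rate for WI-NRS, and no precision for the daily ANCOVA, so there is nothing of the plan's own to reproduce. The stated power concerns vIGA-AD success and does not bear on this point.

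**Inputs from the documents.** One daily baseline score; up to 7 pre-treatment scores (SAP 5.2); about 650 children randomized 2:1 (SAP 5.1, 3.1).

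**Assumed inputs.** R = single-day reliability, 0.6 to 0.8. c = correlation of true itch between baseline and follow-up, 0.5 to 0.7, with 0.3 as a weak case. a = day-to-day autocorrelation of the within-child deviations, 0 or 0.4, with 0.8 as a strong case. Randomized vIGA-AD score is left out; any part of the gain that it already captures would shrink the figures.

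**Formulas.** Scale one day's score to variance 1.
- Covariance of two baseline days i and j: R + (1 - R)·a^|i-j|
- Covariance of a baseline day with a later day, d days apart: c·R + (1 - R)·a^d
- The variance of the treatment difference is proportional to the residual variance, 1 - q'B⁻¹q. Here B is the covariance matrix of the covariates and q is their covariance with the outcome.
- Variance ratio = residual variance with both covariates / residual variance with the single score.

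**Case a = 0.** The mean then carries all the baseline information, and the ratio is [1 - c²R²/(R + (1 - R)/7)] / [1 - c²R²].
- R = 0.6, c = 0.7: c²R² = 0.1764 and R + 0.4/7 = 0.6571, so (1 - 0.2684)/(1 - 0.1764) = 0.7316/0.8236 = **0.89**.
- R = 0.8, c = 0.5: c²R² = 0.16 and R + 0.2/7 = 0.8286, so (1 - 0.1931)/(1 - 0.16) = 0.8069/0.84 = **0.96**.

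**Case a = 0.4, R = 0.8, c = 0.5, 7 days after the last baseline score.** q = (0.4003, 0.4001) for single score and mean. B has variances 1 and 0.8576 and covariance 0.8475. The residual variance is 0.8397 with the single score and 0.8132 with both, a ratio of **0.97**.

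**Variance ratio, both covariates versus single score (R 0.6-0.8):**

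| Assumption | 1 day after baseline | 7 days | 28 days |
|---|---|---|---|
| a = 0, c = 0.5-0.7 | 0.89-0.96 | 0.89-0.96 | 0.89-0.96 |
| a = 0.4, c = 0.5-0.7 | 0.98-1.00 | 0.91-0.97 | 0.91-0.97 |
| a = 0.8, c = 0.5-0.7 | 0.99-1.00 | 0.98-0.99 | 0.96-0.98 |
| a = 0-0.8, c = 0.3 | 0.98-1.00 | 0.98-1.00 | 0.98-1.00 |

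A simulation with 433 and 217 children and integer 0-10 scores, with a = 0 or 0.4 and c = 0.5 or 0.7, gave the same range: 0.89-0.97 at Day 7.

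**Conversion.** √0.89 = 0.943 and √0.97 = 0.985, so the standard error falls by about 6% to 1.5%. 1/0.89 = 1.12 and 1/0.97 = 1.03, equivalent to about 12% to 3% more children.

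**Adding versus replacing.** With a = 0.4 and c = 0.5-0.7, putting the mean in place of the single score raises the variance on the first day by 3-7%. If the outcome stays change from the daily baseline, a plain swap does worse. With days equally correlated, residual variance rises by 8-40% in the cases tried. Keeping the daily baseline avoids both problems: change and raw score then give the same treatment estimate and standard error.

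**Cost in degrees of freedom.** With 650 children the present model leaves 650 - 4 = 646 and the extended one 645, a cost of about 1/645 = 0.2% in variance.

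**The case against.** The strongest reply is that nothing here is an error. Adjusting change from baseline for that same baseline is the matching choice, it is applied uniformly to every continuous exploratory endpoint, and no other section contradicts it. The estimate is valid either way. Weekly itch already has the 7-day average as its baseline, and the daily p-values are nominal. All of this stands, and it makes the point an optional improvement.

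The size is also open to challenge. With autocorrelation 0.8 and true-itch correlation 0.5-0.7 the gain is about 0.5-2% at Day 7; with true-itch correlation 0.3 it is 0-2%. On the first days, where a reader would look for onset, it can be close to nothing. So the documents do not support an inference that the intervals are materially too wide on most days. Nor do they assign the daily series the task of showing onset.

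Two further inferences are tempting and fail. One is that the model adjusts for a single diary score and nothing else; it also contains the randomized vIGA-AD score. The other is that the single score has no merit. It keeps children with 1-3 baseline diaries in an observed-data analysis, whereas the SAP's average is missing for them. If those children were dropped, a variance ratio (present over new) of 1.10 would be cancelled by losing 1 - 1/1.10 = 9% of children.

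That last argument tells against using the 4-of-7 average as it stands. It does not tell against a mean of whatever scores are available.

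**Conclusion.** The point holds as a modest gain in efficiency. The only itch covariate in the daily ANCOVA is one diary score, and a 7-day mean can be added from data already collected. Under the central assumptions (reliability 0.6-0.8, true-itch correlation 0.5-0.7, autocorrelation 0-0.4) the variance of the treatment difference in change from baseline falls by about 3-11% from about Day 7, or about 1.5-6% in standard error. Under stronger autocorrelation or weaker baseline-to-follow-up correlation the gain may be near zero. No structure tried showed a loss from adding the mean, apart from the degree of freedom.

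These figures rest on assumed correlations, because the documents give none. Percent change from baseline, also an endpoint, was not computed, and the size there may differ. A reader might infer bias or an inflated error rate; neither follows. Much larger gains appear only if true itch is assumed perfectly correlated between baseline and follow-up (c = 1), for which the documents offer no support in a treatment trial.

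**What to change.** In SAP 12.3, for daily WI-NRS only, state that the ANCOVA contains treatment, randomized vIGA-AD score, daily baseline WI-NRS and, as a second covariate, the mean of the WI-NRS scores in the 7 days before treatment.

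For this covariate only, take the mean of all scores available in those 7 days even when there are fewer than 4. Name it as a separate variable, because SAP 4.4 and 5.2 reserve the average weekly baseline for children with at least 4 of 7 diaries. That definition should stay unchanged for the WI-NRS population, the weekly analysis and WI-NRS success. WI-NRS is also recorded at Screening, so a child's last score could predate the 7 days; setting the new covariate to the daily baseline there keeps that child in the model too.

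The cost is one degree of freedom, one derived variable with its own missing-data rule, and a sentence or two in the SAP. No new data are needed. The change should be made before unblinding, so that the choice of covariate cannot appear data-driven.

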Similar multiple imputation method will be used for the EASI total score (refer to Section 5.5) where the missing EASI total score data at Weeks 1, 2, and 4 will be imputed, not the missing EASI question score data. Since the missing EASI total scores have a precision of 1 decimal place, the MCMC imputation for the non-monotone missing data will be restricted to values between 0 and 72, rounded to the 1st decimal (i.e., 0.1). Imputation of missing data for EASI total score will be based on the ITT population.

Even though it is only considered an exploratory endpoint, the multiple imputation methods will also be applied to the weekly average WI-NRS score at Weeks 1, 2, 3, and 4. The MCMC imputation for the non-monotone missing data will be restricted to values between 0 and 10, rounded to the 1st decimal (i.e., 0.1). Imputation of missing data for average weekly WI-NRS score will include all subjects in the ITT population.

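### Mean EASI and weekly WI-NRS are compared on observed cases only, with no missing-data sensitivity analysis, although the SAP already multiply imputes both scores

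*SAP*

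**What the plan says.** **Continuous analysis.** SAP 12.3 analyses change and percent change at each visit "using an analysis of covariance (ANCOVA) with the factors of treatment, randomized vIGA-AD score, and baseline of the variable under analysis as covariate". On the data used it says: "These analyses will be performed based on observed data in the ITT population". It plans no imputation, repeated-measures model or missing-data sensitivity analysis for these comparisons.

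**Imputation already planned.** SAP 6.2.1: "Similar multiple imputation method will be used for the EASI total score", "where the missing EASI total score data at Weeks 1, 2, and 4 will be imputed". For itch, "the multiple imputation methods will also be applied to the weekly average WI-NRS score at Weeks 1, 2, 3, and 4". Both are done on the ITT population. The regression step uses treatment and the child's earlier scores.

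**Where the imputed scores go.** SAP 12.3 says the exploratory categorical endpoints will "be analyzed by visit and treatment group based on MI data and the ITT population". EASI-75 at Week 4, a secondary endpoint, also uses them (SAP 12.2, Table 5). The continuous comparisons do not.

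**Adverse-event and lack-of-efficacy leavers.** For these children SAP 12.3 states that "efficacy data assigned to a pre-specified analysis visit will be removed from observed data" from the visit window containing the last dose onward.

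**Status.** SAP 12.3: "The p-values will be nominal as no formal inferential testing will be done on exploratory efficacy endpoints".

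**The concern.** A visit-wise ANCOVA on observed cases uses the baseline score and stratum but not the child's own Week 1 and Week 2 scores. It is safe if loss is random or explained by baseline, stratum and arm. It is not safe if children who do badly after baseline leave, and do so more in one arm than the other.

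The plan itself regards some loss as informative. Protocol 8.2.1 says so for discontinuation due to an adverse event or lack of efficacy, and SAP 12.1.1 classes those children as missing not at random. For the binary endpoints they count as non-responders. For the continuous endpoints their values are taken out and nothing replaces them.

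At stake is the coherence of the report. EASI-75 and mean EASI at the same visit would rest on different children and different missing-data assumptions, and the reader would have no check on the mean difference.

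**Working it through.** **The plan's own figure.** None is given for mean EASI or WI-NRS. The nearest is power above 90% for the primary endpoint (22% vs 37%, 217 vs 433, two-sided 0.025). The pooled rate is (433×0.37 + 217×0.22)/650 = 0.320, so the null SE is 0.0388 and the alternative SE 0.0365. Power = Φ[(0.15 − 2.241×0.0388)/0.0365] = Φ(1.73) = 95.8%, which agrees. It does not bear on the continuous scores.

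**Inputs.** From the documents: 433 and 217 children, the ANCOVA terms, and the imputation terms. Assumed: scores in SD units with higher worse; correlation 0.6 between all visits; true differences of 0.15, 0.25 and 0.40 SD at Weeks 1, 2 and 4; loss of 5% to 20% per arm; and log-odds of loss rising by 1 (moderate) or 2 (strong) per SD of worse Week 2 score. The vIGA-AD stratum is left out.

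**Standard error.** Residual SD after baseline = √(1 − 0.6²) = 0.8. SE = 0.8 × √(1/433 + 1/217) = 0.0665 SD.

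**Hand check.** Let d be the loss in an arm and g the baseline-adjusted amount by which leavers would have scored worse at Week 4 than their whole arm. The mean of those who stay differs from the full mean by −g × d/(1 − d). With the same g in both arms, the bias in active minus vehicle is

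g × [d_V/(1 − d_V) − d_A/(1 − d_A)].

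Take g = 0.2 SD. At 5%/15%: 0.2 × (0.1765 − 0.0526) = 0.025 SD, or 6% of 0.40.

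**Simulation.** Each scenario used 1.5 million children, 2:1. Each range runs from moderate to strong dependence on the Week 2 score.

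| Loss active/vehicle | Hand check (g = 0.2) | Observed-case difference (truth −0.40) | Bias, % of effect | Bias in SE |
|---|---|---|---|---|
| 5%/5% | 0 | −0.40 | 0 | 0 |
| 5%/10% | 0.012 | −0.387 to −0.383 | 3–4% too small | 0.2–0.3 |
| 5%/15% | 0.025 | −0.379 to −0.369 | 5–8% too small | 0.3–0.5 |
| 5%/20% | 0.039 | −0.368 to −0.352 | 8–12% too small | 0.5–0.7 |
| 15%/5% | −0.025 | −0.422 to −0.431 | 5–8% too large | 0.3–0.5 |

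Further results:

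- Imputing Week 4 from treatment and all earlier scores (as in SAP 6.2.1 step 2, but with normal draws instead of predictive mean matching) came within 0.3% of the truth in every row.
- Unequal loss that was completely random (5%/15%), or driven only by baseline (4%/13%), gave no bias.
- With no true effect and Week 2-driven loss of 4%/14%, observed cases showed a false 0.03 SD in favour of vehicle.
- If loss depends on the unseen Week 4 score itself (5%/15%), observed cases are 14–21% too small and imputation is still 11–17% too small.

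**Sensitivity to the correlation.** With 0.8 throughout, the bias is 2–3% at 5%/10% and 5–8% at 5%/20%. With 0.3 to baseline and 0.7 between later visits, it is 7–10% at 5%/10% and 19–29% at 5%/20%. The mechanism is firm; the percentage depends on inputs that the documents do not give.

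**The case against.** **No planned conclusion depends on this.** The endpoints are exploratory, outside the testing hierarchy, and have nominal p-values. Protocol 5.2.2 lists no continuous EASI or WI-NRS endpoint. This stands and limits the weight of the point. Yet SAP 6.2.1 imputes weekly WI-NRS while acknowledging that it is exploratory, so that status is no reason to leave the imputed scores unused.

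**Unequal, response-driven loss is not shown.** A reader might infer it from the ban on rescue medication (Protocol 6.9). The documents give no rate or direction, and several features favour retention: entry to the extension requires the Week 4 visit (Protocol 2, footnote o), leavers are scheduled for Week 4 assessments (Protocol 7.5), and early-termination data from Days 23 to 43 can count as Week 4 (SAP 5.4), except where the removal rule applies. This stands, so the claim is conditional.

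**A matched comparison exists.** EASI-75 is also analysed on observed data, so a reader can set it beside observed mean EASI. True, but that gives no mean difference under another missing-data assumption.

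**Imputation would not fully align the two endpoints.** This stands. Values of adverse-event and lack-of-efficacy leavers are removed before imputation, so on the continuous scale they would be imputed as missing at random, whereas EASI-75 counts them as failures. Hence the sensitivity analysis in the fix.

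**Conclusion.** The point holds as a low-cost improvement. The only planned comparison of mean EASI and weekly WI-NRS is one that goes wrong if loss depends on post-baseline response and differs between arms, while a method that removes this bias under missing at random is already being prepared. With assumed correlation 0.6, the bias is roughly 5% to 12% of the effect (0.3 to 0.7 SE) at 5%/15% to 5%/20% loss and smaller at 5%/10%. It is about zero if loss is equal and equally selective in both arms, or unrelated to response.

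Three stronger readings are not supported:

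- That the trial's efficacy conclusions are at risk. The primary and secondary analyses do not use this method.
- That observed cases flatter the active cream. If more poor responders leave vehicle, the effect shrinks; it grows only if more leave active.
- That every continuous scale needs a new longitudinal model. Protocol 8.2.2 calls for descriptive analysis of CDLQI, IDQoL, DFI, SCORAD and POEM, and no imputation is planned for them.

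**What to change.** In SAP 12.3, for change and percent change in EASI total score and average weekly WI-NRS only:

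1. Run the stated ANCOVA (treatment, randomized vIGA-AD score, baseline) on each imputed dataset produced under SAP 6.2.1 and combine by Rubin's rules.
2. Keep the observed-case ANCOVA as supportive.
3. State that step 1 imputes adverse-event and lack-of-efficacy leavers under missing at random, unlike the non-responder rule for EASI-75.
4. Add a simple delta-adjusted or reference-based sensitivity analysis for those children.
5. State how children without a weekly WI-NRS baseline are handled, since SAP 6.2.1 names only post-baseline weeks for imputation.

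Leave the other scales as planned. The cost is SAP wording, a little programming on datasets already planned, and one more set of tables.
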